- Individuals will be recruited as soon as IRB approval is obtained and will continue until target sample size (n=10) is reached or when project period ends on December 31, 2022.
- Individuals will be recruited from the Boston area, and patients being treated for OUD at BWH affiliated clinical programs.
- OUD is present in about 3% of Massachusetts residents, and we have over 500 active OUD patients across BWH affiliated clinical programs with OUD and therefore should be able to reach recruitment target.
- At our clinical sites, Black and Latino patients are over-represented, and therefore our study will likely recruit an ethnically and racially diverse participant population.

5. Subject Enrollment

Adults with a DSM-5 diagnosis of OUD and who are currently in treatment with buprenorphine or methadone will be recruited. Patients with OUD at Brigham and Women's Hospital (BWH) and Brigham and Women's Faulkner (BWF) will be referred to study staff by their health care providers at these clinical sites for possible inclusion. Their health care providers, who will be known to the potential subject and will have first-hand knowledge of the patient's medical history, will (1) first give approval for his/her patient to be contacted/approached for research purposes, (2) initially introduce the study to the patient, and (3) obtain the patient's permission, verbally during the course of providing medical care, to be contacted by study staff. Subjects will also be recruited from the Partners Clinical Trials website, <http://Rally.partners.org>, as well as print advertisements and flyers posted at the clinics. Study visits will be conducted at the BWH Center for Clinical Investigation. Study staff will perform a preliminary screen on the telephone or virtually to establish suitability for the study. If suitable, a study staff will schedule the individual for a baseline visit which will be performed remotely or in-person. Informed consent will be obtained at the baseline visit in-person or remotely, after which the full inclusion and exclusion criteria will be applied. For remote consenting, study staff will utilize the Mass General Brigham REDCap eConsent. Those who meet criteria will then be randomized to either CBD first or placebo first, and scheduled for the two study visits.

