6. STUDY PROCEDURES

Overall approach: A total of 3 study visits are planned (**Table 1**) The first visit is the baseline visit, and the other two are double-blind placebo-controlled medication visits, where either CBD or placebo will be administered. Participants will be randomized using a random-number generator in a 1:1 ratio of CBD to placebo. During the baseline visit, after obtaining informed consent, participants will complete the baseline assessments. The subject will then be scheduled for their study visits 2 and 3 during which they will receive CBD or placebo in random order in double-blind fashion. Visits 2 and 3 will be scheduled at

Research Consent Form**General Consent Form Template****Version Date: February 2021**

Subject Identification

least 1 week apart to function as a washout. Baseline visit will take no longer than an hour, and the subsequent visits will take no more than 2 hours to complete.

Visit 1: Baseline

Participants will provide written informed consent, obtained by the PI or another study physician. The blood and urine samples collected during the Baseline Visit will be used for inclusion/exclusion purposes. Specifically, participants who are currently pregnant (as confirmed by the pregnancy test), or have hepatic liver enzymes greater than three times the upper normal limit (as confirmed by the liver function tests, or LFTs) will be excluded. Subjects will also complete baseline PHQ9, GAD7, BPI, TLFB, COWS, PANAS, and opioid cravings.

Visit 2: CBD or placebo

After arrival to the study site, the participant will receive either the CBD 600mg or placebo, immediately followed by obtaining baseline heart rate, blood pressure, PHQ9, GAD, BPI, TLFB, COWS, opioid cravings, and urine sample for toxicology testing. Heart rate and blood pressure will be monitored every 30 minutes (vital signs: heart rate, blood pressure) following receipt of CBD or placebo. At 60 minutes following the CBD or placebo administration, the participant will then proceed to complete the cue-reactivity test, visual probe task, Iowa gambling task, monetary choice questionnaire (MCQ), and the mirror tracing persistence task (MTPT). Just prior to and after the MTPT task, subjects will provide saliva sample and complete the positive and negative affect scale (PANAS). An additional saliva sample will be collected 20 minutes after the MTPT task.

Visit 3: CBD or placebo

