The same procedures for Visit 2 will be repeated during visit 3, scheduled at least 1 week after visit 2. The order in which CBD or placebo is administered will be randomized.

Cannabidiol:

Research Consent Form

General Consent Form Template

Version Date: February 2021

Subject Identification

Subjects will receive 600mg of oral CBD or matching placebo. Cannabidiol will be provided using Epidiolex™ oral solution 100mg/mL. Drug will be procured by the BWH Investigational Drug Services (IDS) pharmacy and the pharmacy at Rutland Regional Medical Center. The CBD or matching placebo will be placed in oral syringes for the subjects to self-administer at the study site. CBD will be stored at room temperature (68 to 77 F) in its original bottle and in an upright position. Once opened, CBD has a shelf life of 84 days.

Primary Outcome: The primary outcomes is the change in cue-induced cravings (Opioid Craving Scale).

Secondary Outcomes: The secondary outcomes are impulsive decision making (Iowa Gambling Task, Monetary Choice Questionnaire), attentional bias (Visual Probe Task), and physiologic and subjective stress-reactivity.

Assessments:

- Patient Health Questionnaire 9-item (PHQ9): Assessment of depressive symptoms
- Generalized Anxiety Disorder 7-item (GAD7): Assessment of anxiety symptoms
- Brief Pain Inventory (BPI): Pain severity and interference assessment.
- Time-line follow back (TLFB): A method of assessing for recent substance use using a calendar.
- Clinical Opioid Withdrawal Scale (COWS): Assessment of opioid withdrawal.
- Opioid craving scale¹²: A 3-item tool to assess current cravings, cravings when exposed to triggers, and likelihood of using if placed in an environment that the individual previous used opioids.
- Cue-induced craving¹³: Participants will be shown both illicit opioid-related and neutral images on a computer screen for one minute each using a standardized protocol. The order in which the cues will be presented will be randomized and counter balanced. Participants will rate their cravings on a visual analog scale. The cue exposure procedure will end with a standardized debriefing exercise. It is important to note that cue-exposure is a safe paradigm for studying craving in this population when employing debriefing procedures.

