No benefits can be guaranteed from participation in the study. However, all enrolled participants will be receiving an adjunctive agent that is hypothesized to help reduce cue-induced cravings associated with their opioid use disorder, and it is possible that at least some subjects will experience a decrease in the severity of their cravings or stress-reactivity. An extensive screening procedure will ensure that individuals entering the trial will have no contraindications. Trained research personnel will perform all study procedures to minimize risks, discomforts, and adverse effects. Buprenorphine and methadone treatment are FDA-approved treatment for the treatment of OUD, and reduces illicit opioid use and related morbidities associated with OUD. This study will generate valuable information about the effect of combining cannabidiol with stable doses of buprenorphine or methadone for patients with OUD. The results will help inform the direction needed to take in developing effective strategies to improve the care of OUD patients taking medications. If successful, this line of research has the potential to significantly impact clinical practice of treating OUD by providing a viable medication adjunct to existing evidenced-based therapies.

9. Statistical Analysis

For all analyses, descriptive statistics will be used to summarize the data. All comparisons will utilize paired t-tests or non-parametric tests where appropriate. Alpha will be set at 0.05 for all analyses.

Primary outcome:

- Cue-reactivity: Cue-reactivity will be defined as the difference between baseline craving scores and the craving scores in response to opioid-related or neutral cues.

Secondary outcome:

- Subjective cravings: Craving scores will be rated on a 0 to 10 visual analog scale for each of the 3 items.
- Attentional bias: This is calculated as the difference in reaction time (RT) between when the probe replaced the neutral compared with the opioid-related images (i.e. RTneutral – RTopiod).
- Delayed discounting: Based on their responses to the MCQ, the rate of discounting, or k value, is calculated, which range from 0.00016 to 0.25. Higher values indicate greater discounting and impulsivity.

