- Impulsive decision making: A net score from the IGT is calculated by subtracting the number of disadvantageous selections from the number of advantageous selections (i.e. (C+D) - (A+B)), where negative scores indicate decision-making that favors immediate rewards despite negative consequences.

Research Consent Form

General Consent Form Template

Version Date: February 2021

Subject Identification

- Distress tolerance: This is measured as the length of time in number of seconds that participants engage in the third MTPT task.
- Subjective stress reactivity: Subjective stress reactivity will be calculated as the difference in the negative affect score from PANAS before and after the stressor task.
- Physiologic stress reactivity: Physiologic stress reactivity will be calculated as the difference in salivary cortisol levels and skin conductance before and after the stressor task.

Power analysis: The estimated mean change in cue-induced cravings scores from prior studies is -1.5 (SD 1.5). Based on this estimate, and a conservative estimate of a correlation of $r=0.60$ between the two time points, a sample size of 10 is needed for 88% power and two-tailed alpha set at 0.05 for a paired-samples t-test. A point estimate of the difference in the change and the 95% confidence interval will be reported. Conversely, if the change in cravings is not normally distributed, then a sum rank test will be used.

10. Monitoring and Quality Assurance

INSTRUCTIONS

Delete grey Instructions box upon completion of this section

Describe the plans that will be followed by study staff for monitoring and quality assurance, including:

- Adverse event criteria and reporting procedures
- Planned safety monitoring, e.g., data monitoring committee (DMC)/data and safety monitoring board (DSMB), independent monitor, PI-monitored, etc., including planned frequency of review. If DMC/DSMB monitored, include either charter as separate attachment or complete DMC/DSMB [APPENDIX](#)
- Outcomes monitoring, including planned frequency of review.
- Study stopping rules as applicable
- Internal monitoring of source data, protocol adherence, and recordkeeping, including which staff will be responsible and planned frequency of review
- Independent monitoring of source data as applicable

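### The non-normal fallback for the primary outcome names no paired test, although the crossover is sized with a paired t-test

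*Combined protocol and SAP*

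**What the plan says.** The design is a two-treatment crossover. Section 5 (Subject Enrollment) states: "Those who meet criteria will then be randomized to either CBD first or placebo first". Section 6 (Study Procedures, overall approach) says of the two medication visits that "they will receive CBD or placebo in random order in double-blind fashion". Every participant therefore supplies a pair of values.

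Section 9 (Statistical Analysis, power analysis) takes a mean change of -1.5, an SD of 1.5 and a correlation of 0.60, and concludes that "a sample size of 10 is needed for 88% power and two-tailed alpha set at 0.05 for a paired-samples t-test". It continues: "A point estimate of the difference in the change and the 95% confidence interval will be reported". The fallback for the primary outcome follows: "if the change in cravings is not normally distributed, then a sum rank test will be used".

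The only other text on the choice of test opens Section 9: "All comparisons will utilize paired t-tests or non-parametric tests where appropriate". No section names a signed-rank test or any other paired rank test, and none says how normality will be judged.

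On the scale, Section 6 says of the cue task: "Participants will rate their cravings on a visual analog scale". Section 9 says of subjective cravings: "Craving scores will be rated on a 0 to 10 visual analog scale for each of the 3 items". Neither states the recording precision.

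**The concern.** The phrase used for the fallback is not the name of a test. The nearest standard name is the Wilcoxon rank-sum (Mann-Whitney) test, which compares two independent groups. Applied here to 10 CBD values against 10 placebo values, it would discard the within-person pairing on which the sample size rests.

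Three readings are open: a slip for the signed-rank test, a literal 10 v 10 rank-sum test, or a rank-sum test of period differences between the CBD-first and placebo-first sequences. The last keeps the pairing, but the plan does not describe it. The three can give different p-values from the same ten people. The primary p-value should not depend on which one the analyst picks after seeing the data.

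**Working it through.** **Inputs from Section 9.** n = 10 pairs, difference 1.5, SD 1.5 (taken per condition), r = 0.60, two-sided alpha 0.05.

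**The plan's own figure.** SD of the differences = 1.5 × √(2 × (1 − 0.60)) = 1.342. Standardised difference = 1.5 / 1.342 = 1.118. Noncentrality = 1.118 × √10 = 3.54 on 9 df. Exact noncentral-t power is 88.1%, which matches the stated 88%. The figure is right, and it depends on the pairing.

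**Direction of the literal reading.** For means, an unpaired analysis takes the variance of the difference to be 2 × 1.5² / 10 = 0.45. With r = 0.60 it is 0.45 × (1 − 0.60) = 0.18. A test that assumes too large a variance rejects a true null too rarely. For the rank test, the size of this effect was found by simulation.

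**Test applied to every trial, normal data** (100,000 replicates, exact critical values). Type I error: signed-rank 0.050, rank-sum 0.005. Power: signed-rank 86.7%, rank-sum 53.5%. These are not the trial's operating characteristics, because the fallback is meant only for non-normal data.

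**Whole procedure: paired t-test, or the fallback if normality is rejected.** The plan gives no normality check, so Shapiro-Wilk at 0.05 on the 10 differences is assumed. The data shapes are also assumed. There were 20,000 replicates per shape, with exact null distributions. RS = literal rank-sum; SR = signed-rank. Conflict means that the fallback is used, the paired t-test has p < 0.05 and the rank-sum test does not.

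| Shape | Null rejection, RS alone | Fallback used | Power when fallback used, RS v SR | Whole-procedure type I error, RS v SR | Whole-procedure power, RS v SR | Conflict |
|---|---|---|---|---|---|---|
| Normal | 0.0043 | 0.050 | 0.53 v 0.87 | 0.047 v 0.049 | 0.865 v 0.882 | 0.019 |
| Laplace | 0.0044 | 0.097 | 0.62 v 0.76 | 0.043 v 0.048 | 0.857 v 0.870 | 0.021 |
| Exponential | 0.0056 | 0.153 | 0.68 v 0.73 | 0.040 v 0.049 | 0.854 v 0.861 | 0.025 |
| t, 3 df | 0.0059 | 0.151 | 0.71 v 0.70 | 0.040 v 0.047 | 0.895 v 0.894 | 0.018 |
| Correlated exponential margins | 0.0030 | 0.204 | 0.78 v 0.73 | 0.034 v 0.046 | 0.875 v 0.863 | 0.021 |
| Log-normal | 0.0066 | 0.337 | 0.84 v 0.72 | 0.028 v 0.047 | 0.916 v 0.874 | 0.021 |

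The power differences (RS minus SR) are -1.7, -1.3, -0.7, +0.1, +1.2 and +4.2 points.

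**Scores held to 0–10, assumed placebo means 5, 3 and 2** (12,000 replicates).
- Continuous scores: fallback used in 4.8%, 5.1% and 6.9% of trials; power 0.862 v 0.877, 0.855 v 0.870 and 0.793 v 0.821; conflict 1.6%, 1.7% and 2.9%.
- Whole-point scores, a further assumption: fallback used in 23.2%, 24.6% and 32.6%; power 0.767 v 0.835, 0.734 v 0.812 and 0.647 v 0.735, which is 7 to 9 points lower; conflict 8.1%, 9.6% and 13.3%.

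**Two-sequence rank-sum test on period differences** (5 v 5 assumed, normal data). Attained type I error is about 3% and power 77%. It is valid, but it is a different test from the other two.

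**The case against.** The strongest reply is that this is a terminology slip. The fallback is triggered by the distribution of one change variable, which is what a signed-rank test takes. The same paragraph fixes a paired t-test and a within-person correlation. Section 9 opens by asking for non-parametric tests only where appropriate, and a test that ignores pairing is hardly appropriate in a crossover. This makes signed-rank the likelier intention. It does not put the test in the plan: in the general sentence the word paired attaches to the t-test, and the more specific sentence names something else.

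Several points on size stand:
- The 0.5% error rate describes the rank-sum test alone, not the trial's procedure, and the error is conservative.
- The 53.5% v 86.7% contrast must not be quoted as the impact.
- The effect on power is small and of mixed sign. It also depends on how a shape is built: another construction of bivariate t data with 3 df used the fallback in 19% of trials and gave power of 90.7% with rank-sum against 89.7% with signed-rank.
- The larger whole-point figures need a recording rule that the plan does not state. With scores to 0.1, also an assumption, the losses were 1.1, 1.2 and 2.8 points, close to the continuous case.
- The conflict with the confidence interval may never be reported, because the word that opens the fallback sentence can be read as confining the interval to the normal case.
- Naming the rank test does not settle how normality is judged, so some choice between the t-test and the rank test would remain.

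**Conclusion.** The concern holds, and it is minor. As written, the primary fallback names no paired test in a paired design. Its nearest standard reading is miscalibrated at about 0.3–0.7% instead of 5% when r = 0.60.

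For the whole procedure with continuous unbounded data, type I error is 2.8–4.7% against 4.6–4.9% with signed-rank, and power is between 1.7 points lower and 4.2 points higher. With continuous 0–10 scores the loss is 1.5 to 2.8 points. A loss of 7 to 9 points arises only if ratings are recorded in whole points. These ranges rest on the assumed Shapiro-Wilk check and the assumed data shapes.

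No inflation of false positives follows, and the sample-size calculation is correct. That the wording names no paired test is certain; that an unpaired test was intended is not.

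**What to change.** In Section 9, power analysis, replace the fallback phrase with: *a Wilcoxon signed-rank test on the within-person CBD-minus-placebo differences, with an exact or permutation p-value, and zero differences and ties handled by the Pratt method with mid-ranks; normality is judged on these differences*. The name of the test and the variable it is applied to are the essential part. The handling of zeros and ties is a useful detail that matters mainly if scores are coarse. Adding the normality check and its threshold would also close the remaining choice between the t-test and the rank test.

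If a rank-sum test of period differences between the CBD-first and placebo-first sequences was meant, describe that test explicitly instead.

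The sample size of 10 and the 88% power need no change. Using the same wording for the secondary outcomes is optional. The cost is one phrase of text, with no patients, visits or money.

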APPENDIX A

Data Monitoring Committee / Data and Safety Monitoring Board Appendix

Research Consent Form

General Consent Form Template

Version Date: February 2021

Subject Identification

- *To be completed for studies monitored by Data Monitoring Committee (DMC) or Data and Safety Monitoring Board (DSMB) if a full DMC/DSMB charter is not available at the time of initial IRB review.*
- *DMC/DSMB Charter and/or Roster can be submitted to the IRB later via Amendment, though these are not required.*

A Data Monitoring Committee (DMC) or Data and Safety Monitoring Board (DSMB) will be convened for safety monitoring of this research study. The following characteristics describe the DMC/DSMB convened for this study (Check all that apply):

- The DMC/DSMB is independent from the study team and study sponsor.
- A process has been implemented to ensure absence of conflicts of interest by DMC/DSMB members.
- The DMC/DSMB has the authority to intervene on study progress in the event of safety concerns, e.g., to suspend or terminate a study if new safety concerns have been identified or need to be investigated.

- Describe number and types of (i.e., qualifications of) members:

The PI will serve as the data monitor given the small size of the study and low risk associated the use of a single dose of CBD. Given that this study will enroll a total of 10 subjects to receive a single dose of CBD 600mg or placebo, that study end points are not serious events (i.e. cue-reactivity), the risks associated with CBD is low, and that the study is completed rather quickly, the PI will serve as the data monitor. The PI will promptly report any adverse events to the IRB and the FDA where appropriate.

- Describe planned frequency of meetings:

Click or tap here to enter text.

- DMC/DSMB reports with no findings (i.e., “continue without modifications”) will be submitted to the IRB at the time of Continuing Review.
- DMC/DSMB reports with findings/modifications required will be submitted promptly (within 5 business days/7 calendar days of becoming aware) to the IRB as an Other Event.
